5.4 DERIVED VARIABLES

ETDRS Score and LogMAR (on chart and off chart)

- ETDRS score is calculated by the examiner and written on the source documents and entered in the eCRF.
- LogMAR (on chart and off chart) will all be derived in eCRF from the Snellen/decimal acuity.
 - I. 1 ETDRS line = 5 letters
 - II. 1 ETDRS line = 0.1 LogMAR
 - III. 0.1 LogMAR = 5 ETDRS letters
 - IV. 15 ETDRS letters = 0.3 LogMAR
 - V. A less positive/more negative LogMAR is an improvement of vision
 - VI. An increase in the number of ETDRS letters read is an improvement of vision
- On-Chart subjects: defined as being able to read at least 3 ETDRS letters on a single line on the ETDRS chart at either 4 or 1 meters
 - a. Have an obtainable Snellen equivalent obtained directly from ETDRS chart

- b. Each Snellen equivalent is assigned a LogMAR value. A Snellen score of 6/6, 20/20, indicating that an observer can resolve details as small as 1 minute of visual angle, corresponds to a LogMAR of 0, since the base-10 logarithm of 1 is 0. A Snellen score of 6/12, 20/40, indicating an observer can resolve details as small as 2 minutes of visual angle, corresponds to a LogMAR of 0.3, since the base-10 logarithm of 2 is near-approximately 0.3, and so on.
- Off-chart subjects: defined as a subject who cannot read at least 3 ETDRS letters on a single line of the ETDRS chart at 1 meter and thus have no Snellen equivalent obtainable from ETDRS chart
 - a. These subjects are categorized as able to either count fingers (CF), detect hand motion (HM), detect light perception (LP), or are no-light perception (NLP).
 - b. If there is no CF and HM and a subject's visual acuity is light perception, then a LogMAR value of 4 will be assigned. If a subject's visual acuity is no light perception, then a LogMAR value of 4.5 will be assigned.
 - c. For those categorized as CF a LogMAR value of 2 will be assigned (Lange equivalence)
 - d. For those categorized as HM a LogMAR value of 2.3 will be assigned (Lange equivalence).

LogCS

Contrast sensitivity was assessed using the Pelli-Robson chart for low vision, on a scale from zero to 2.5 LogCS. Subjects who could not read at least 2 out of the first 3 letters on the Pelli-Robson chart will be assigned the worst possible score (a LogCS of zero).

- LogCS is obtained based on which letter triplets the subject can read correctly on the chart, and the LogCS value is then entered in the eCRF.

Nadir of LogCS

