Nadir of LogCS is defined for each eye of each subject as the worst LogCS observed from baseline to the visit of interest, including baseline and visit of interest values.

If contrast sensitivity is off-chart at any time point in the study, the first off-chart LogCS value will be considered to be the nadir, with the applied equivalence of LogCS 0.

BCVA and HVF

- Best-corrected visual acuity (BCVA), Humphrey Visual Field 30-2 (HVF) and Spectral Domain Optical Coherence Tomography (SD-OCT) will be assessed and then recorded on the eCRF.

Nadir of BCVA

The Nadir of BCVA is defined for each eye of each subject as the worst BCVA observed from baseline to the visit of interest, including baseline and visit of interest values. The first occurrence of this value will be considered as Nadir.

Responder Definitions

Eye Responder

- Definition 1: An improvement of at least 15 Early Treatment Diabetic Retinopathy Study (ETDRS) letters (equivalent to a decrease of at least 0.3 LogMAR) compared to baseline, or having a Snellen acuity equivalent better than 20/200 (equivalent to 1 LogMAR).
- Definition 2: Eyes that lose less than the 15 ETDRS letters (equivalent to an increase of less than 0.3 LogMAR) compared to baseline.

Subject Responder

- A subject will be considered a responder if the ETDRS score of the treated eye is at least 15 ETDRS letters better than the sham eye, or if the treated eye has a LogMAR acuity at least 0.3 LogMAR better than the sham eye, at a given visit (2, 2.5, 3, 4 and 5 years).

Vision Loss Duration at the Time of Treatment

- Vision loss duration in days will be based on the difference between the date of onset of vision loss of the first affected eye and baseline date (last BCVA non-missing value prior to the start time of treatment administration in the RESCUE/REVERSE studies).
- Vision loss duration will also be calculated for the second affected eye.

Treatment-Emergent Adverse Events (TEAE)

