7. INTERIM ANALYSES

Two interim analyses are planned at completion of Visit 3 (Year 3) and Visit 4 (Year 4), in addition to the final analysis at Year 5. The final results based on all time points will be included in the final Clinical Study Report (CSR).

No Data Monitoring Committee (DMC) will be assembled for evaluation of results in this long-term follow-up study.

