8.5.2 Secondary Efficacy Variables

8.5.2.1 Pelli-Robson Contrast Sensitivity

Eye Level

Contrast Sensitivity will be summarized at each follow-up visit (Years 2, 3, 4, and 5), along with change from baseline to each follow-up visit.

This summary will be done comparing all-GS010 eyes to all-sham eyes.

These summary tables will be reproduced for eyes with on-chart LogCS at baseline, with off-chart LogCS at baseline (equivalence LogCS 0), and for all eyes.

The change of LogCS from baseline to the visit of interest will be compared between all-GS010 treated eyes and all-Sham treated eyes.

At each visit of interest, the following analyses related to Nadir LogCS will be performed:

- The change from Nadir LogCS will be calculated for each eye of each subject and will be expressed in LogCS.
- The time to Nadir LogCS will be calculated for each eye of each subject and will be expressed in Weeks.
- The mean LogCS change from Nadir will be assessed for all eyes, all GS010 eyes and all-Sham eyes.
- The mean time to Nadir LogCS will be assessed for all eyes, all GS010 eyes and all-Sham eyes.

Subject Level

At subject level, the best outcome (change from Baseline or change from Nadir) observed in either eye will be considered. The following summaries will be presented:

- The change of LogCS from baseline to the visit of interest
- The change of LogCS from Nadir to the visit of interest

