The following responders analyses will be performed on all eyes, all GS010 eyes and all sham eyes.

- Eyes with an improvement of at least 0.3 LogCS compared to baseline.
- Eyes with an improvement of at least 0.3 LogCS compared to nadir LogCS.
- For eyes with on-chart LogCS at baseline, an improvement of at least 0.3 LogCS compared to baseline.

- Switch from baseline off-chart LogCS to on-chart at visit of interest

Subject Level – Subject Responder

At subject level, the best outcome observed in either eye will be considered.

LogMAR

Subject Responder analyses will be carried out at visit of interest for the following definitions:

- Subjects with CRR from baseline in at least one eye at visit of interest.
- Subjects with CRR from nadir in at least one eye at visit of interest.
- Subjects with an improvement of at least -0.3 logMAR compared to baseline in at least one eye at visit of interest.
- Subjects with an improvement of at least -0.3 LogMAR compared to nadir in at least one eye at visit of interest.
- Subjects with an improvement of at least -0.2 logMAR compared to baseline in at least one eye at visit of interest.
- Subjects with an improvement of at least -0.2 logMAR compared to nadir in at least one eye at visit of interest.
- Subject with LogMAR BCVA value $\leq +1.0$ LogMAR in at least one eye at visit of interest.
- Subject with LogMAR BCVA value $< +1.0$ LogMAR in at least one eye at visit of interest.
- For patients with both eyes off-chart at baseline, switch from baseline to on-chart (LogMAR ≤ 1.6) in at least one eye at visit of interest
- Number/percentage of on-chart patients (at least one eye on-chart) at visit of interest
- Clinically Relevant stabilization (CRS): Patient having a LogMAR < 1.0 at baseline in at least one eye that was maintained in this eye at the time point of interest (final BCVA)
- Clinically Relevant Benefit (CRB): Treatment benefit manifests as a clinically relevant stabilization (CRS) or a clinically relevant recovery (CRR) from nadir or both

For the subject responder endpoint, a randomization test will be performed for each of the follow-up visits (Years 2, 2.5, 3, 4 and 5):

- Response status of subjects whose ETDRS scores of the treated eye are at least 15 letters better than the sham eye or whose treated eye has a LogMAR acuity of at least 0.3 LogMAR better than the sham eye at each long-term follow-up visit.

LogCS

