Subject Responder analyses will be carried out at visit of interest for the following definitions:

- Subjects with an improvement of at least 0.3 LogCS compared to baseline in at least one eye.
- Subjects with an improvement of at least 0.3 LogCS compared to nadir LogCS in at least one eye.
- For subjects with both eyes off-chart LogCS at baseline, switch from baseline to on-chart LogCS in at least one eye at visit of interest

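### SAP 5.4 gives the LogCS nadir two conflicting time windows, and its fixed off-chart LogMAR values depart from protocol 9.6.5 without an entry in SAP 8.8

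*SAP*

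**What the plan says.** **LogCS nadir.** SAP 5.4 defines it for each eye as "the worst LogCS observed from baseline to the visit of interest, including baseline and visit of interest values". The next sentence reads: "If contrast sensitivity is off-chart at any time point in the study, the first off-chart LogCS value will be considered to be the nadir". Such a value is scored as 0. The BCVA nadir in the same section has the same window, and its added sentence only settles repeated values: "The first occurrence of this value will be considered as Nadir".

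The LogCS nadir is used at each visit of interest in three places:
- SAP 8.5.2.1, change from nadir and its timing: "The time to Nadir LogCS will be calculated for each eye of each subject and will be expressed in Weeks".
- SAP 8.5.2.4, eye level: "Eyes with an improvement of at least 0.3 LogCS compared to nadir LogCS".
- SAP 8.5.2.4, subject level: "Subjects with an improvement of at least 0.3 LogCS compared to nadir LogCS in at least one eye".

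**Off-chart LogMAR.** Protocol 9.6.5 obtains LogMAR for count fingers (CF) and hand motion (HM) from an equation that takes the examiner's finger or hand dimensions and the test distance. SAP 5.4 uses constants instead: "For those categorized as CF a LogMAR value of 2 will be assigned", and 2.3 for HM. It also assigns 4 to light perception (LP) and 4.5 to no light perception (NLP), for which the protocol gives no LogMAR value. SAP 8.8 lists the changes from the protocol, down to added OCT graphics, and states that they do not contradict it. The CF/HM derivation is not on the list.

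**The concern.** The two LogCS sentences use different windows: one stops at the visit analysed, the other runs over the whole study. An eye that first goes off-chart after a given visit gets a different nadir at that visit depending on which sentence the programmer follows. Under the second, information from the future enters an earlier result, and an eye that never improved can be reported as improved.

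For off-chart acuity, what is at stake is a declared secondary endpoint: subject response, meaning a treated eye at least 15 letters or 0.3 LogMAR better than the sham eye (protocol 7.2.2, endpoint 5; SAP 4.3). Off-chart eyes have no ETDRS score (protocol 9.6.5), so when both eyes are off-chart only the LogMAR limb can decide it. Replacing a distance-based value with a constant can change that decision, and a reader of 8.8 would not know that the replacement was made.

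**Working it through.** The plan gives no sample size or event count to reproduce. Its one relevant conversion does reproduce: 15 letters × 0.02 LogMAR per letter = 0.30 LogMAR.

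**1. LogCS nadir**

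Inputs: off-chart is coded 0, the floor of the 0 to 2.5 scale (SAP 5.4). The responder threshold is 0.3 LogCS (SAP 8.5.2.4). Contrast visits are Years 2, 3, 4 and 5 (SAP 8.5.2.1). The eye profiles are assumed, because the documents hold no subject data.

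Let m be the worst value from baseline to visit v.
- Bounded reading: change from nadir = LogCS(v) − m.
- Literal reading, for an eye first off-chart after v: change = LogCS(v) − 0.
- The literal reading inflates the change by m. It creates an extra responder whenever LogCS(v) ≥ 0.3 and LogCS(v) − m < 0.3.

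| Assumed eye | Visit | LogCS | Bounded change | Literal change | Responder (bounded / literal) |
|---|---|---|---|---|---|
| Stable: 0.60 at baseline, off-chart at Year 5 | Years 2, 3, 4 | 0.60 | 0.00 | +0.60 | no / yes |
| Worsening: 0.60 at baseline, off-chart at Year 5 | Year 2 | 0.45 | 0.00 | +0.45 | no / yes |
| | Year 3 | 0.45 | 0.00 | +0.45 | no / yes |
| | Year 4 | 0.30 | 0.00 | +0.30 | no / yes |
| Either eye | Year 5 | 0 | 0.00 | 0.00 | no / no |

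Timing of the nadir under the literal reading: Year 5 = 5 × 365.25/7 = 260.9 weeks, Year 4 = 208.7, Year 3 = 156.5, and the Year 2 visit is week 96. The nadir would fall 260.9 − 96 = 164.9, 260.9 − 156.5 = 104.4 and 260.9 − 208.7 = 52.2 weeks after the Year 2, 3 and 4 visits.

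An eye that is off-chart at or before the visit gets the same nadir either way, because 0 is already the worst possible value. At Year 5, the last visit, the two readings agree for every eye.

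**2. Off-chart LogMAR**

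Gaps between the fixed values (CF 2.0, HM 2.3, LP 4.0, NLP 4.5): CF–HM 0.3, LP–NLP 0.5, HM–LP 1.7, CF–LP 2.0, HM–NLP 2.2, CF–NLP 2.5. Only CF–HM sits on the 0.3 threshold. Two eyes in the same category always differ by 0.

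With the constants, a treated eye at CF beside a sham eye at HM is therefore a subject responder whatever the test distances. Under the protocol method, the result depends on dimensions and distance.

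The equation is not printed in the documents. Assume that LogMAR changes with log10 of distance for the same fingers. Then two CF eyes tested at 1 m and 2 m differ by log10(2) = 0.301, and at 0.5 m and 2 m by log10(4) = 0.602. If the treated eye is the better one, each pair is a responder under the equation and a non-responder under the constants, where the gap is 0.

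The sensitivity analysis in SAP 8.7.1, which drops off-chart tests beyond 2 m, covers only the eye-level endpoints of 8.5.2.2. It does not check this responder endpoint.

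**The case against.** **The nadir sentence has a sensible reading.** Within the window an off-chart zero is already the worst value, so the second sentence may only say which zero counts, as the BCVA rule does. A nadir dated after the visit analysed makes little sense, which is itself a reason to prefer that reading. This stands, and it rules out saying that the LogCS nadir is plainly unbounded. What remains is that the words name the whole study, while the BCVA rule does the same job without them. Independent programming (SAP 9) may expose a disagreement but would not say which reading was intended.

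**Interim results.** A reader might infer that the Year 3 and Year 4 interim results were affected and later revised. The documents do not show this. The SAP is Version 2.0 of 30 June 2022, and nothing shows that either interim used this rule.

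**The exact tie.** A reader might infer that a difference of exactly 0.3 is left undefined. It is not: the responder definition says at least 0.3, so it counts. Unrounded double precision stores 2.3 − 2.0 as 0.2999999999999998, but that is a programming matter. A two-decimal rounding rule is not a safe remedy. SAP 5.4 derives LogMAR from Snellen or decimal acuity, and if those are true logarithms (an assumption), 20/125 against 20/63 gives log10(125/63) = 0.2976, which rounding would turn into a responder difference.

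**Bias.** A reader might infer that the constants favour GS010. They apply equally to treated and sham eyes, and by the working above they can remove responders as well as create them. No direction is shown.

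**Unseen detail.** Protocol 9.6.5 leaves full details to an SOP. It also says that off-chart eyes have no LogMAR before saying how one is obtained. That strengthens the case for reconciling the texts; it does not supply the missing 8.8 entry.

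**Conclusion.** Both parts hold, and both are minor.

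1. The two LogCS nadir sentences conflict as written. The literal reading can make an eye that never improved a from-nadir responder at Years 2 to 4, by the full amount of its bounded nadir (0.60 in the stable example). From-nadir LogCS outcomes are not declared endpoints.
2. The CF and HM constants are a real and unlisted departure from protocol 9.6.5. Because their gap equals the 0.3 threshold, the choice of derivation can decide subject response for pairs of off-chart eyes. LP and NLP are not part of the conflict, since the SAP values there fill a gap.

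The number of affected eyes and any between-arm effect cannot be stated from the documents. The eye profiles and the log-distance form are assumptions used for illustration. The affected efficacy analyses are secondary or added, with no multiplicity adjustment (SAP 8.5.4). Year 5 LogCS, all from-baseline LogCS results and the primary safety endpoint do not change under part 1, and part 2 does not touch safety.

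**What to change.** 1. Replace the off-chart nadir sentence in SAP 5.4 with: *If contrast sensitivity is off-chart at any time point from baseline to the visit of interest, the first such value (LogCS 0) is the nadir.*
2. Reconcile protocol 9.6.5 with SAP 5.4, state which CF/HM derivation is used, and list it in SAP 8.8 with the reason. At the same time, settle the SAP 5.4 statement that off-chart LogMAR comes from Snellen or decimal acuity, since that section also says off-chart eyes have no Snellen equivalent from the chart.
3. Ask that programs treat a difference of exactly 0.3 as meeting the threshold of at least 0.3. No new rounding rule or extra responder table is needed.

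The cost is one reworded sentence, one clarification with an 8.8 entry, and a programming check. No endpoint changes and no new data are needed. The nadir rewording has no evident downside.

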In the RESCUE/REVERSE studies, both eyes received standard antiseptic preparation, were administered topical local ocular anesthetic agents, and had pupillary dilation. Administration of an intraocular pressure-lowering agent preceded treatment. GS010 was administered once during the study via a single intravitreal (IVT) injection. Sham IVT injection was performed by applying pressure to the eye at the location of a typical procedure using the blunt end of a syringe without a needle. The right eye of each subject was randomly allocated to receive either GS010 or sham treatment in a 1:1 allocation ratio. The fellow (left) eye received the treatment not allocated to the right eye. Therefore, each subject received GS010 in one eye and sham treatment in the fellow eye.

The schema of the study design of the RESCUE/REVERSE studies is given below:

[figure not shown]

An algorithm with a testing hierarchy was employed to determine the best- and worst-seeing eye of each subject prior to randomization. The randomization was based on the right and left eye, because if the right eye was treated, the left eye would receive sham and vice versa, so the treatments were automatically balanced. However, the best- or worst-seeing eye at entry could have been a confounding factor, and it could not be excluded that the treatment effect would not be the same in the best and worst seeing-eye. In order to test this hypothesis with optimal power, an adaptive randomization technique called Efron's minimization¹⁰ method was used to minimize the imbalance of treatment groups between the best-seeing eyes and worst-seeing eyes.

Masking was accomplished with sham injection of the fellow eye. Thus, treatment allocation was double-masked for both the subject and the investigation (follow-up) team, except the physician and medical team that performed the GS010 administration and sham injection and the first follow-up visit. Centralized analysis of the Early Treatment Diabetic Retinopathy Study (ETDRS) visual acuity results, automated visual fields, SD-OCT, color vision and contrast sensitivity was performed by a masked central reading lab.

The schematic design of this long-term follow-up non-interventional study is given below:

Figure 1: Study Design Schematic of the Long-Term Follow-up of Subjects from the RESCUE and REVERSE Clinical Studies

Note: Inclusion into the long-term follow-up study will be allowed from Week 96 of the RESCUE/REVERSE studies up to 1 day prior to Year 2.5.

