3.4 RANDOMIZATION

This study does not include any randomization, as the treatment (GS010/sham) was randomized in the prior REVERSE/RESCUE studies. The right eye of each subject was randomly allocated to receive either GS010 or sham treatment in a 1:1 ratio. The fellow (left) eye received the treatment not allocated to the right eye.

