4.3 SECONDARY EFFICACY ENDPOINTS

The secondary efficacy endpoints are:

- Change in contrast sensitivity measured with the Pelli-Robson chart in all-, best-, and worst-eyes treated with GS010 IVT injection compared to all-, best-, and worst-eyes treated with sham IVT injection respectively to the follow-up study time points (2, 3, 4, and 5 years).
- Change in best-corrected visual acuity (BCVA) reported with Logarithm of the Minimal Angle of Resolution (LogMAR), change of parameters measured with Humphrey™ visual field (HVF) 30-2, and change of parameters measured with spectral-domain optical coherence tomography (SD-OCT) in all-, best- and worst-eyes treated with GS010 IVT injection compared to all-, best-, and worst-eyes treated with sham IVT injection respectively to each follow-up study time points (2, 2.5, 3, 4, and 5 years).
- Response status of eyes treated with GS010 IVT injection compared to eyes treated with sham IVT injection, including all-, best- and worst-eyes receiving GS010 or sham respectively, with responder eyes defined by:
 - An improvement of at least 15 ETDRS letters (equivalent to a decrease of at least 0.3 LogMAR) compared to baseline, or having a Snellen acuity equivalent better than 20/200.
 - Eyes that lose less than the 15 ETDRS letters (equivalent to an increase of less than 0.3 LogMAR) compared to baseline.
- Response status of subjects whose ETDRS scores of the treated eye are at least 15 letters better than the sham eye or whose treated eye has a LogMAR acuity of at least 0.3 LogMAR better than the sham eye at each long-term follow-up visit (2, 2.5, 3, 4, and 5 years).
- Visual improvement as measured by LogMAR to determine the difference in improvement (LogMAR) for all-GS010 eyes compared to all-sham eyes, for best-GS010 eyes compared

to best-sham eyes, and for worst-GS010 eyes compared to worst-sham eyes, with comparisons to baseline at each follow-up study time point (2, 2.5, 3, 4, and 5 years).

- Change of ganglion cell layer (GCL) volume and other parameters measured by SD-OCT for all-GS010 eyes compared to all-sham eyes, for best-GS010 eyes compared to best-sham eyes, and for worst-GS010 eyes compared with baseline at each follow-up study time point (2, 2.5, 3, 4, and 5 years).
- QoL as measured with the Visual Functioning Questionnaire 25 (VFQ-25), with change from baseline at each follow-up study time point (2, 2.5, 3, 4, and 5 years).

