4.4 PREDETERMINED COVARIATES AND PROGNOSTIC FACTORS

GCL thickness/volume and topographical maps, best or worst-seeing eye (eye status) as determined prior to randomization and duration of vision loss at the time of treatment could be significant prognostic factors for the treatment effect.

The baseline LogMAR will also be used as a covariate for analysis of change in LogMAR. Similarly, the baseline of the endpoint being analyzed will be used as the model's covariate.

The investigative site will not be included in the analysis as the number of subjects recruited per site will be very small. However, stratification by geographical area may be performed as a sensitivity analysis. Neighboring countries can be pooled to reach at least 9 subjects per geographical entity. All analysis will be performed using an alpha of 0.05 (two-sided test).

These covariates will be used in the analyses presented in [Section 9.5 Efficacy Analysis](#).

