8. STATISTICAL METHODS

All analyses will be performed on SAS Version 9.4 or higher.

Unless otherwise noted, categorical and binary variables will be summarized using counts and percentages. Percentages will be rounded to one decimal place.

Continuous variables will be summarized using the number of observations (n), mean, standard deviation (SD), median, first quartile (Q1), third quartile (Q3), minimum and maximum. Change from baseline or from nadir will also be summarized by a 95% confidence interval (CI).

Least square means, 95% CIs, and p-values will be reported from ANCOVA models. Estimated proportions with 95% CIs will be provided for Generalized Estimating Equation (GEE) models and for logistic regression models for responder endpoints. ANCOVA models will be run on all continuous endpoints, logistic regression for all subject responder endpoints, and GEE models for all eye responder endpoints.

Rounding rules are generally as follows:

- If the original variable has x decimal places, then minimum and maximum will be reported with x decimal places; mean, median, Q1, Q3, SD and CIs will be reported with x+1 decimal places.
- P-values will be reported with four decimal places.

Summary TFLs will display standard headers containing the sponsor name (“GenSight Biologics”) as well as a standard footer containing the name of the program used to generate the display, its path, and a date stamp. Headers, footers, titles, and column headers for tables will be repeated on every page of each display; pages will be numbered “Page x of y.” Visit labels in tables and figures will show visit name. Summary TFLs containing no applicable data will display a line reading, “No applicable data were reported” or similar wording. Dates and times will be presented using SAS DATE9. and SAS TIME5. formats.

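### The subject responder compares the two eyes at the visit and ignores their baseline gap, so its raw percentage is not a treatment response rate; report the mirror-image count and a baseline-adjusted version beside it

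*SAP*

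**What the plan says.** The endpoint appears in SAP section 4.3 as "Response status of subjects whose ETDRS scores of the treated eye are at least 15 letters better than the sham eye", with a LogMAR alternative. SAP section 5.4 repeats it: a subject responds on the letter criterion, or "if the treated eye has a LogMAR acuity at least 0.3 LogMAR better than the sham eye, at a given visit". Protocol section 7.2.2, item 5, and SAP section 8.5.2.4 agree. None of these refers to the eyes' baseline values.

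The eye responder in SAP section 5.4 does refer to baseline. Definition 1 reads in part "equivalent to a decrease of at least 0.3 LogMAR) compared to baseline, or having a Snellen acuity equivalent better than 20/200", and Definition 2 limits loss relative to baseline.

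On testing, SAP section 8.5.2.4 states: "For the subject responder endpoint, a randomization test will be performed for each of the follow-up visits". SAP section 8 instead plans "logistic regression for all subject responder endpoints, and GEE models for all eye responder endpoints". SAP section 4.4 adds: "All analysis will be performed using an alpha of 0.05 (two-sided test").

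On allocation, SAP section 3.4 says: "The right eye of each subject was randomly allocated to receive either GS010 or sham treatment in a 1:1 ratio". SAP section 3.1 adds that Efron's minimization "was used to minimize the imbalance of treatment groups between the best-seeing eyes and worst-seeing eyes".

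**The concern.** A responder rate is normally read as the share of subjects who benefited. Here it mixes benefit with starting position. The documents make starting gaps plausible: protocol section 5.1 describes sequential vision loss, and SAP section 3.1 designates a best and a worst eye before randomization and calls that status a possible confounder.

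Off-chart coding adds a direct route. SAP section 5.4 assigns 2.0 LogMAR to count fingers and 2.3 to hand motion, so an unchanging one-category gap in favour of the treated eye meets the 0.3 threshold at every visit.

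The plan controls for baseline elsewhere. The LogMAR models carry it as a covariate, and SAP section 8.8 justifies replacing the McNemar and Fisher tests partly because the new models can control for it. It does not mention the between-eye subject responder.

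At stake is the meaning of a percentage that will be reported at five time points, by study and pooled.

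**Working it through.** The plan states no expected responder rate, power or number of subjects for this endpoint, so there is no figure to reproduce.

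**Inputs from the documents.** Threshold 0.3 LogMAR (SAP 5.4); two-sided alpha 0.05 (SAP 4.4); 1:1 allocation of the right eye with best/worst-eye minimization (SAP 3.1, 3.4).

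**Assumptions, not in the documents.** Baseline between-eye SD sB = 0.2 to 0.6; noise SD sE = 0.3 to 0.4; persistence r of the baseline gap from 0.3 to 1; N = 60 and a true effect δ = 0.2 LogMAR for the power illustration; normal distributions.

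**Model.** Let B be the baseline difference, treated minus sham (lower is better).

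- At the visit: D = r·B + E − δ, with SD(D) = √(r²sB² + sE²).
- On change: C = D − B, with SD(C) = √((1−r)²sB² + sE²).
- No-effect responder rate = Φ(−0.3/SD).

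**Step 1: no-effect rate with the gap fully persisting (r = 1).**

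- At visit, lowest: SD = √(0.04 + 0.09) = 0.361; Φ(−0.832) = 20%.
- At visit, highest: SD = √(0.36 + 0.16) = 0.721; Φ(−0.416) = 34%.
- On change: Φ(−0.3/0.3) = 16% to Φ(−0.3/0.4) = 23%.

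Much of the no-effect rate is therefore follow-up noise, which a change rule does not remove.

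**Step 2: what the mirror count shows.** Take sB = 0.4, sE = 0.3, r = 1, so SD(D) = 0.5. With no effect, Φ(−0.6) = 27.4% favour each eye; net 0. With δ = 0.2, Φ(−0.1/0.5) = 42.1% favour the treated eye and Φ(−0.5/0.5) = 15.9% the sham eye; net 26.2 points. The 42.1% alone does not reveal how much is effect.

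**Step 3: validity.** With no effect, subjects with a gap of at least 0.3 fall equally on either side in expectation. Under independent 1:1 allocation the randomization test is an exact sign test among them. Its two-sided type I error is 2.2% to 3.7% over a wider grid (N 30 to 75, r 0 to 1, sE up to 0.5). Simulated values at N = 60 are 3.2% to 4.7%.

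**Step 4: power.** SD(D) = SD(C) when r² = (1−r)², that is r = 0.5. Exact sign test, N = 60, sE = 0.3, δ = 0.2, independent allocation:

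| r | sB | No-effect rate, visit / change | Power, visit / change |
|---|---|---|---|
| 0.8 | 0.2 | 18.9% / 16.1% | 96% / 98% |
| 0.8 | 0.4 | 24.7% / 16.7% | 83% / 98% |
| 0.8 | 0.6 | 29.8% / 17.7% | 62% / 97% |
| 0.5 | any | identical | identical |
| 0.3 | 0.4 | 17.7% / 23.2% | 97% / 88% |
| 0.3 | 0.6 | 19.6% / 28.1% | 95% / 70% |

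**Step 5: balanced allocation.** A simulation (2,000 trials, 1,000 re-randomizations each) used an Efron biased coin on the best eye, with probability 2/3 assumed, and re-randomized the same way. At r = 0.8 the power, visit versus change, is 94% versus 99% (sB 0.4) and 87% versus 98% (sB 0.6). Subtracting r·B rather than all of B gives about 98% to 99% in every δ = 0.2 setting simulated.

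**The case against.** A reader might infer that the definition produces false-positive results. It does not: step 3 shows the test holds its level, because a pre-existing gap is as likely to favour sham as treatment.

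A reader might also infer that power is lost. That needs more than half of the baseline gap to persist if the comparator is simple change, and the documents point both ways. SAP section 1 cites a natural-history study in which 86% of patients had stable eyes, which favours persistence. Protocol section 5.1 reports bilateral involvement in 80% of a cohort within 6 months and, in other reports, in more than 97% of patients at 12 months. A gap caused by sequential onset should therefore shrink well before Year 2. No persistence figure is given.

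A third tempting step is to replace the definition by a difference in change. Below r = 0.5 that lowers power and raises the no-effect rate, and it would redefine a protocol endpoint under a SAP finalized on 30 June 2022.

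It is also fair to say that baseline is handled in neighbouring analyses: the LogMAR ANCOVA, the eye responder definitions, and the best-versus-best and worst-versus-worst comparisons. This is one unadjusted secondary endpoint with no power claim, and balanced allocation recovers part of any loss if the test reflects it. All of that stands and limits the weight of the point. It does not make the percentage interpretable.

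**Conclusion.** The point holds as one of definition and reporting. A static pre-treatment gap of 0.3 LogMAR counts as a response, and a gap of the same size the other way demands a relative shift of 0.6, which treated-eye gain or sham-eye decline can supply. The raw percentage is therefore not a treatment response rate: about 20% to 34% would respond with no effect under the assumed SDs and full persistence, against 16% to 23% on change. These ranges rest wholly on assumed values.

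No general claim about power is supported. Against simple change the definition is weaker if r exceeds 0.5, equal at 0.5 and stronger below it. Within this model only a weighted baseline adjustment does well throughout.

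Two gaps in specification add to this. SAP sections 8 and 8.5.2.4 name different methods for the same endpoint, and the re-randomization scheme is not stated. Every subject received both treatments, so a proportion estimated by logistic regression has no comparison group, and its no-effect value is unknown.

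**What to change.** 1. Keep the protocol definition. At each visit, report beside it the mirror-image count (sham eye at least 0.3 LogMAR or 15 letters better) and the net difference.
2. Add a supportive analysis of the between-eye difference at the visit, adjusted for the baseline between-eye difference with the weight estimated from the data. Give the change-based responder as a further description only.
3. State that the randomization test re-randomizes under the actual best/worst-eye minimization used in RESCUE and REVERSE.
4. Amend SAP section 8 or 8.5.2.4 so that one method is named for this endpoint.

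Both eyes' baselines are already defined in SAP section 5.2, so no new data are needed. The cost is a few SAP sentences, a few extra table rows and one more unadjusted secondary analysis, to be labelled supportive.
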